Annually, approximately 15 million babies worldwide are born preterm [1, 2]. Preterm birth is a leading cause of neonatal mortality and morbidity [3]. Cervical insufficiency is one factor implicated in the complex mechanisms involved in spontaneous preterm birth [4]. Cervical insufficiency is characterized by acute and painless dilatation of cervix in absence of uterine contractions resulting in the inability of cervix to retain a pregnancy to term. Insertion of a cervical cerclage suture can be used to treat cervical insufficiency. A cervical cerclage is a mechanical support to the cervix, where a surgical band or string is applied around the cervix to prevent preterm opening of the cervix, and thereby preventing preterm birth. It can be applied either vaginally or trans-abdominally. The latter can be applied either by laparoscopic or open access surgery. Growing evidence support that both open access and laparoscopic cerclage procedures are safe and effective [5]. Still, many aspects of the abdominal cerclage remains uncertain. Recently, a study by Ades et al. was published on the obstetric outcome of subsequent pregnancies in women from an Australian single-center cohort who had a laparoscopic cerclage left in situ [6]. They reported on 22 women who became pregnant a second or third time after a laparoscopic cerclage. The authors encouraged other groups to report their obstetric outcomes on subsequent pregnancies after laparoscopic cerclage in order to gather a larger data material to describe this gap in evidence. Therefore, we plan to study the obstetric outcome from the first and subsequent pregnancies after laparoscopic cerclage in a Danish cohort from Aarhus University Hospital in a 10 years' period.

Objective

In a Danish cohort, to investigate the obstetric outcome after laparoscopic cerclage placement in the first and subsequent pregnancies.

Material and Methods

Study type

Observational study based on medical chart review.

Eligibility criteria

Women who underwent laparoscopic cerclage at Aarhus University Hospital, Denmark between May 2011 and May 2021. Trachelectomy prior to the laparoscopic cerclage is defined as an exclusion criteria.

The laparoscopic cerclage procedure

The surgical method of the laparoscopic cerclage procedure at Aarhus University Hospital is previously described in a paper by Riiskjaer et al [7]. The primary surgeon has been one of three laparoscopic surgeons with a long experience in performance of the procedure.

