- History of three or more spontaneous miscarriages/deliveries between 14+0 and 36+6 weeks
- Other (free text)

Characteristics of the surgical procedure

- Additional procedures performed during surgery (e.g. hysteroscopy, removal of endometriosis)
- Performed in Day Surgery (yes/no)
- Date of surgery (dd-mm-yyyy)
- Early complications from the laparoscopic cerclage (follow-up time is 30 days from the procedure):
 - Conversion to laparotomy during surgery (yes/no)
 - Haemorrhage > 500 ml (yes/no)
 - Postoperative infection treated at hospital (yes/no)
 - Damage to internal organs (yes/no)
 - Need for re-operation (yes/no)
 - Admission to Intensive Care Unit (yes/no)
 - Thromboembolic events (defined as deep vein thrombosis, pulmonary embolism or stroke) (yes/no)
 - Maternal cardiopulmonary arrest (yes/no)
 - Maternal death (yes/no)
- Late complications from the laparoscopic cerclage (follow-up in the entire period of data collection subsequent to the laparoscopic cerclage):
 - Erosion into the vagina treated in hospital (yes/no)
 - Pain complaints from the stiches leading to intervention in pregnancy (yes/no)
 - Other complications from the cerclage leading to intervention in hospital (free text)

For every known/confirmed pregnancy subsequent** to the laparoscopic cerclage (follow-up in the entire period of data collection subsequent to the laparoscopic cerclage):*

**defined as a pregnancy confirmed by urine and/or serum hcg and/or ultrasound AND described in the medical record*

***If the laparoscopic cerclage was performed in early pregnancy, this pregnancy is the first pregnancy for data collection*

- Pregnancy;
 - Maternal age (years)
 - Parity (numerical)
 - Conceivement (Spontaneous/Assisted Reproductive Technologies)
 - Certain gestational age, defined as gestational age determined by Crown-Rump-Length (yes/no)
 - Gestation (singleton/multiple)

- Treatment with vaginal progesterone (yes/no)
- At miscarriage or delivery;
 - Gestational age (weeks and days)
 - If gestational age < 22 weeks and 0 days of gestation;
 - Need for operative surgery in connection with miscarriage (yes/no)
 - If gestational age ≥ 22 weeks and 0 days;
 - Administration of lung maturation < 34 weeks of gestation (yes/no)
 - Administration of tocolytics < 34 weeks of gestation (yes/no)
 - Chorioamnionitis (defined as antibiotic treatment or intervention leading to delivery)

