- Indication for delivery (spontaneous labor contractions/PPROM/PROM/obstetric indication/abdominal cerclage as indication for delivery)

Outcomes

The outcomes of this study apply to a set of core outcomes for evaluation of interventions to prevent preterm birth leaving out the late neurodevelopmental morbidity [8].

Maternal:

- Pregnancy and delivery (follow-up in the entire period of data collection subsequent to the laparoscopic cerclage):
 - Time from the laparoscopic cerclage to first known/confirmed pregnancy (counting from the first day in pregnancy based on results from ultrasonography if available, otherwise on the date of her last menstrual period)
 - Pregnancies subsequent to the laparoscopic cerclage (numerical)
 - Miscarriages
 - Early miscarriages (< 16 weeks and 0 days)
 - Late miscarriages (< 22 weeks and 0 days)
 - Deliveries < 28 weeks and 0 days of an infant living at time of discharge from hospital
 - Deliveries < 32 weeks and 0 days of an infant living at time of discharge from hospital
 - Deliveries < 34 weeks and 0 days of an infant living at time of discharge from hospital
 - Deliveries < 37 weeks and 0 days of an infant living at time of discharge from hospital
 - Uterine rupture (yes/no)

Neonatal:

The following neonatal outcomes are reported for neonates delivered with a gestational age ≥ 20 weeks and 0 days.

- Gestational age (weeks and days)
- Birthweight (g) (follow-up at delivery)
- Neonatal survival (defined as survival at time of discharge from hospital)
- Survival with major neonatal morbidity (time point: at discharge from hospital)
 - Necrotising enterocolitis (NEC)

- Bronchopulmonary Dysplasia (BPD) (defined as respiratory/oxygen support at postmenstrual age (PMA) 36 weeks)
- Intraventricular haemorrhage (IVH) Grade III and IV
- Hydrocephalus with ventriculoperitoneal (VP) shunt
- Periventricular leukomalacia
- Retinopathy of prematurity (ROP)

Statistical analysis plan

Statistics will be descriptive and data will be presented with counts and percentages for categorical variables, mean and standard deviation for continuous Gaussian distributed variables, and median and interquartile range for continuous non-Gaussian variables. Proportions will be presented with a 95% confidence interval for the dichotomous outcomes '*neonatal survival*' and '*neonatal survival without major neonatal morbidity*'.

Subgroup analyses of the primary outcome will be undertaken for the following subgroups:

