- Prior versus no prior cesarean delivery at time of laparoscopic abdominal cerclage
- Prior versus no prior conisation at time of laparoscopic abdominal cerclage
- Placement of laparoscopic abdominal cerclage before or during early pregnancy

STATA will be used for data management and analyses.

Data collection

Prior to data collection the relevant authority (Central Denmark Region) will be applied for permission to access the relevant data source. All data is already available and will be extracted from the patients' electronic data records. Women will be identified on the ICD-10 Procedure Code KLDD10B. The follow-up period extends to May 2022 to allow at least one year of follow-up for all procedures. The primary investigator performs a pilot collection of data from the electronic data records of ten random women in the data set giving birth at Aarhus University Hospital. The pilot collection aims to test the accessibility of the variables, the use of the eCRFs, and the time spent. Following the pilot of data collection, the study group meet to adjust the variables if needed.

Data management

All data will be entered in to an eCRF designed for this study using the REDCap database Study. Data will be collected and managed using REDCap electronic data capture tools hosted at Aarhus University [9]. REDCap is a secure, web-based application designed to support data capture for research studies, providing 1) an intuitive interface for validated data entry; 2) audit trails for tracking data manipulation and export procedures; 3) automated export procedures for seamless data downloads to common statistical packages; and 4) procedures for importing data from external sources.

Data will be handled according to all relevant Danish laws including the General Data Protection

Regulation (“Databeskyttelsesforordningen”) and the Data Protection Act (“Databeskyttelsesloven”). The project is registered with the Central Denmark Region’s internal list of research projects.

Publication plan

Results from this study will be published in a peer-reviewed journal.

The principal investigator will draft the paper as first author, and the daily supervisor will be last corresponding author. Additional authorship will follow standard authorship guidelines and will include all members of study group. Authorships of additional publications will depend on the nature of involvement.

Confidentiality

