## Statistical analysis plan

Statistics will be descriptive and data will be presented with counts and percentages for categorical variables, mean and standard deviation for continuous Gaussian distributed variables, and median and interquartile range for continuous non-Gaussian variables. Proportions will be presented with a 95% confidence interval for the dichotomous outcomes.

Subgroup analyses of the primary outcome will be undertaken for the following subgroups:

- Prior versus no prior cesarean delivery at time of laparoscopic cerclage
- Prior versus no prior conisation at time of laparoscopic cerclage
- Placement of laparoscopic abdominal cerclage before or during early pregnancy

STATA will be used for data management and analyses.

Examples of anticipated tables is shown below.

**Table 1.** Maternal Characteristics upon laparoscopic cerclage placement

n	n
Age, years	mean (range)
Smoking	no. (%)
Body Mass Index (kg/m  )	median (interquartile range)
Parity	median (interquartile range)
Previous conization	no. (%)
- 0	no. (%)
- 1 conus	
- 2+	
Previous caesarean delivery	
Performed as emergency caesarean	no. (%)
Previous uterine surgery	no. (%)
Placement of laparoscopic cerclage during pregnancy	no. (%)
Indications for the laparoscopic cerclage placement	
a) Previous emergency/laboring cesarean delivery followed by a spontaneous singleton late miscarriage or preterm birth from 16+0 to 28+0 weeks	no. (%)
b) Previous elective vaginal cerclage placement but nonetheless a spontaneous late miscarriage or preterm birth between 14+0 and 28+0 weeks (= failed vaginal cerclage)	no. (%)
c) Previous ultrasonography-indicated emergency cerclage with preterm birth between 14+0 and 28+0 weeks	no. (%)
d) Conization and a short pre-pregnancy cervix	no. (%)
e) Two or more deliveries in gestational age 16+0 to 28+0 weeks and a clinical diagnosis of cervical insufficiency	no. (%)
f) Three or more deliveries in gestational age 16+0 to 36+6 weeks	no. (%)
g) Others	no. (%)

**Table 2.** Characteristics laparoscopic cerclage procedure

n		n
Additional procedures performed during surgery		no. (%)
Performed in Day Surgery		no. (%)
Year of surgery		
2011 trough 2014		no. (%)
2015 trough 2018		no. (%)
2019 trough 2022		no. (%)
Early complications		
Conversion to laparotomy during surgery		no. (%)
Haemorrhage > 500 ml		no. (%)
Postoperative infection treated at hospital		no. (%)
Damage to internal organs		no. (%)

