Need for re-operation		no. (%)
Admission to Intensive Care Unit		no. (%)
Thromboembolic events		no. (%)
Maternal cardiopulmonary arrest		no. (%)
Maternal death		no. (%)
Late complications		
Erosion into the vagina treated in hospital		no. (%)
Pain complaints from the stiches leading to intervention in pregnancy		no. (%)
Other complications from the cerclage leading to intervention in hospital		no. (%)

**Table 3.** Pregnancy outcomes and neonatal survival subsequent to laparoscopic cerclage placement

Obstetric outcome in pregnancies treated with laparoscopic cerclage  
Statistical analysis plan version 1.0

**Table 4.** Time intervals

n	n
Time from the laparoscopic cerclage to first pregnancy (years and days)	median (IQR)

**Table 5.** Characteristics of live born neonates

n	n
Gestational age at birth	no. (%)
Birth weight (g)	median (IQR)

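### SAP Table 4 gives time from cerclage to first pregnancy as a plain median although potential follow-up runs from 1 to about 11 years, so the figure is biased towards short times

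*SAP*

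**What the plan says.** The protocol (Eligibility criteria) takes in "Women who underwent laparoscopic cerclage at Aarhus University Hospital, Denmark between May 2011 and May 2021". Under Data collection it says: "The follow-up period extends to May 2022 to allow at least one year of follow-up for all procedures". Under Outcomes, Maternal, it lists "Time from the laparoscopic cerclage to first known/confirmed pregnancy", with the event dated by "counting from the first day in pregnancy based on results from ultrasonography if available" and otherwise by the last menstrual period.

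SAP Table 4 has one row of results for this outcome, "Time from the laparoscopic cerclage to first pregnancy (years and days"), summarised as median and interquartile range. That matches the SAP's general rule of "median and interquartile range for continuous non-Gaussian variables".

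Neither document names a time-to-event method or a censoring rule. Neither says how a woman with no recorded pregnancy by May 2022 enters Table 4, and the table's n is not defined.

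**The concern.** This is a time-to-event outcome with staggered entry and a common closing date. A woman operated on in May 2021 can contribute only a time of up to about one year. If she conceives at 18 months she contributes nothing, whereas a woman operated on in May 2011 who conceives at 18 months contributes 1.5 years. Long times are thus selectively lost, which is right truncation, and the bias can only run towards short times.

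At stake is one descriptive figure that may be used in counselling. Read without qualification, the median would suggest that pregnancy follows cerclage sooner than it does in this cohort.

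**Working it through.** **No figure to reproduce.** The documents state no sample size, pregnancy rate or time to pregnancy. Only the follow-up range comes from them. The rest is illustration.

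**Step 1, follow-up range (from the protocol).** Shortest: May 2022 − May 2021 = 1 year. Longest: May 2022 − May 2011 = 11 years. SAP Table 2 has a last surgery-year band labelled "2019 trough 2022", which runs past the end of eligibility. I read it as a rounded label and keep May 2021 as the last date.

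**Step 2, assumptions (not in the documents).**
- Surgery dates are uniform over the ten years, so follow-up C is uniform on 1 to 11 years.
- Time to pregnancy T among eventual conceivers is exponential with median m, so the rate is λ = ln 2 / m.
- T and C are independent.

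**Step 3, share of eventual conceivers seen to conceive.**

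p = 1 − (e^(−λ) − e^(−11λ)) / (10λ)

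For m = 1: λ = 0.693, e^(−λ) = 0.500, e^(−11λ) = 0.0005, so p = 1 − 0.4995/6.931 = 0.928.

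**Step 4, the plain median x.** It solves F(x) = p/2, where F(x) is the probability of conceiving by x and within follow-up.
- For x ≤ 1: F(x) = 1 − e^(−λx).
- For x > 1: F(x) = 1 − e^(−λx)(11 − x)/10 − (e^(−λ) − e^(−λx))/(10λ).

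For m = 1: p/2 = 0.464, so e^(−λx) = 0.536 and x = 0.90 year.

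For m = 2: λ = 0.3466, p = 0.802 and p/2 = 0.401. At x = 1.49, F = 1 − 0.597 × 0.951 − (0.707 − 0.597)/3.466 = 0.401, so x = 1.49 years.

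| True median among eventual conceivers (years) | Share seen to conceive, p | Plain median (years) | Too short by |
|---|---|---|---|
| 0.5 | 0.98 | 0.49 | 3% |
| 1 | 0.93 | 0.90 | 10% |
| 2 | 0.80 | 1.49 | 25% |
| 3 | 0.69 | 1.87 | 38% |

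In time, the shortfall is about 5 weeks at a true median of 1 year (0.10 × 52) and about 6 months at 2 years (0.51 × 12). These percentages do not depend on what share of women ever conceive, because women who never conceive have no value in either median.

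**Step 5, does a censoring method recover the target?** In 1,000 simulated cohorts of 100 women, all eventually conceiving, the typical Kaplan-Meier median was 0.98 against a true 1.0 year, and 2.0 against 2.0 years. If 80% ever conceive, half of all women are pregnant at −m × log2(1 − 0.5/0.8) = 1.42m, that is 1.42 or 2.83 years for m = 1 or 2. Kaplan-Meier gave 1.39 and 2.86.

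**The case against.** **The study is descriptive, and a median among women who conceived is legitimate.** This stands in part. Such a median would be acceptable if labelled, but the Table 4 row carries no such label. Even with a label it would pool women who had 1 year to conceive with women who had 11. A cumulative incidence curve is also descriptive and adds no test.

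**The bias may be trivial.** It may: at a true median of 0.5 year it is about 5 days. The size cannot be known when the plan is fixed, and the correction does no harm if the bias is small.

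**That women without a pregnancy are left out is inferred.** True. The documents are silent, but a woman with no event has no time to enter into a plain median.

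**The remedy has weaknesses.** It does. Intention to conceive is not collected, so women not trying count as at risk. Pregnancies count only if described in the medical record, and no last-contact or migration date is listed, so censoring at May 2022 assumes complete capture to that date. Hysterectomy is not a listed variable, and maternal death appears only as a 30-day complication. These limits need stating. They do not make the plain median preferable.

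**Readings that go too far.**
- A reader might infer that the plan hides how many women never conceived. Table 4 has an n row, the protocol lists the number of subsequent pregnancies as an outcome, the SAP calls its tables examples, and the body of Table 3 was not in the text available for review. Concealment is not shown.
- A reader might infer a spurious shortening over calendar time. No analysis of this outcome by year of surgery is planned; year appears only as counts in SAP Table 2.
- A reader might set the time by which half of all women are pregnant against the plain median and call the whole gap bias. Those are two different quantities; only the shortfall against the median among eventual conceivers is truncation.

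**Conclusion.** The concern holds. The planned summary ignores censoring, and its error has a known direction. The size is unknown. The 3%, 10% and 25% shortfalls rest on exponential times and uniform surgery dates, and would differ under other shapes or uneven accrual.

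The importance is modest. The documents do not rank this outcome explicitly, and its place at the head of the maternal list gives it no special weight. The stated objective is obstetric outcome in pregnancies after cerclage, and the protocol singles out the two neonatal survival outcomes for confidence intervals. I therefore treat it as secondary. Nothing here affects the neonatal results. The change is worth making because it is cheap.

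**What to change.** For women with pre-conception placement, replace the Table 4 row with:

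- The cumulative incidence of first recorded pregnancy at 1, 2 and 5 years, with 95% confidence intervals and numbers at risk, and the median time if it is reached. If no competing events are recorded, this is 1 minus the Kaplan-Meier estimate.
- Women with no recorded pregnancy censored at May 2022.
- Recorded death or hysterectomy treated as a competing event. Censoring it would treat those women as still able to conceive and overstate the cumulative percentage pregnant.
- The number of women with no recorded pregnancy.
- If a plain median is kept, the label: among women with a recorded pregnancy by May 2022.

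The restriction to pre-conception placement is needed because the protocol says: "If the laparoscopic cerclage was performed in early pregnancy, this pregnancy is the first pregnancy for data collection". Those times are zero or negative and would pull the figure down further. With a true median of 1 year and in-pregnancy placement assumed at 12 weeks, the plain median falls from 0.90 to 0.76 year if 10% of placements are of this kind, and to 0.60 if 20% are.

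**Cost.** A short addition to the SAP and standard Stata commands. Surgery date, pregnancy start and cut-off are already in the plan. Death and hysterectomy are used only where the chart records them.

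**Downside, for a footnote.** The estimate is time to recorded pregnancy, not fertility, because intention to conceive is not collected and only pregnancies in the medical record count. It assumes complete capture to May 2022. It will be longer than the plain median.
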